ANCOVA	Analysis of Covariance
BCVA	Best Corrected Visual Acuity
CMH	Cochran Mantel Haenszel
CI	Confidence Interval
CRF	Case Report Form
ET	Early Termination
ITT	Intention to Treat
IOP	Intraocular Pressure
LOCF	Last Observation Carried Forward
MedDRA	Medical Dictionary for Regulatory Activities
OD	Oculus Dexter (Right Eye)
OS	Oculus Sinister (Left Eye)
PK	Pharmacokinetics
PP	Per protocol
SAE	Serious Adverse Event
SD	Standard Deviation
SOC	System Organ Class
SM	Specular Microscopy
TEAE	Treatment Emergent Adverse Event
WHODrug	World Health Organization Drug Dictionary

1 INTRODUCTION

1.1 Trial Objectives

The primary objective of this study is to evaluate the ocular safety of a single dose of AG-920 after topical ocular administration (2 drops 30 seconds apart), with reference to placebo (vehicle), including visual acuity, intraocular pressure, biomicroscopy, and adverse events.

The secondary objective of this study is to evaluate a subset of subjects (approximately 12 subjects receiving AG-920 and 6 subjects receiving placebo) for the effect of AG-920 on corneal endothelial cell count (ECC) using specular microscopy.

This document describes the statistical analysis methods and data presentations for the data analyses of Protocol AG920-CS303. Related documents to this SAP are the study protocol and case report form (CRF or eCRF). Data analysis will be based on the final dataset(s) provided by Sponsor or designee Data Management group, which is [REDACTED].

The study database(s) includes all CRF-based clinical data. The original EDC database constructed by [REDACTED] will be converted into a CDISC SDTM version 3.1 and/or 3.1.1 database. [REDACTED] will provide the treatment code for treatment unmasking after database lock.

1.2 Background Information

Injections of pharmacologic agents into the vitreous cavity for the purpose of treating various disorders of the retina as well as intraocular inflammatory disease have become the mainstream. In almost all cases, these injections are made through the pars plana. An injection into the eye in this location, with the needle oriented properly, will be posterior to the human lens or an intraocular implant, but anterior to the retina, thereby avoiding damage to these important structures. The pars plana is a zone that rings the eye extending from 3.0 mm to 5.5 mm from the edge of the cornea.

While topical agents such as proparacaine achieve excellent anesthesia on the external surface of the eye, they do not numb the internal aspect of the pars plana, which is extremely sensitive. Currently, physicians fall into one of two methodologies: either injecting lidocaine under the conjunctiva first and then executing a second injection through the pars plana, or using topical lidocaine gel and then performing the intravitreal injection. Patients often report moderate to severe discomfort with each of these approaches. Thus, it is important that a new product is developed for physicians to use in assisting the intravitreal injection.

For that purpose, [REDACTED] is evaluating the formulation of articaine, an approved local anesthetic, for topical ocular use to provide local anesthesia for intravitreal injections. The Sponsor intends to develop [REDACTED] (coded named AG-920) for topical ocular use to induce local anesthesia for intravitreal injecti [REDACTED]

In summary, AG-920 is a sterile topical ophthalmic solution made from [REDACTED] for physicians to apply on the pars plana area of the eye to assist performing the intravitreal injection of pharmacologic agents for the treatment of various disorders of the retina.

2 STUDY DESIGN

2.1 Rationale

Refer to Section 1.3 Design Justification of the study protocol (see Protocol No. AG-920-CS303).

2.2 Description of Trial Design

This is a Phase 3, randomized, placebo-controlled, double-masked, parallel-group design study of AG-920 topically administered versus placebo (vehicle) in healthy subjects. The study will evaluate the safety following one dose of [REDACTED] Sterile Topical Ophthalmic Solution (AG-920) in reference to placebo. Eligible subjects will be randomized in a 2:1 ratio to receive a single dose of AG-920 or matching placebo into one eye, designated as subject's study eye. The application of one single dose of AG-920 consists of 2 drops 30 seconds apart into the subject's study eye.

The study consists of two visits and a follow-up phone call: one screening visit on Day -2 to Day 0 (Visit 1), one baseline/assessment visit on Day 1 (Visit 2), and one follow-up phone assessment on Day 2-5 (Phone Follow-Up). In addition, approximately 18 subjects from one site will be asked to return to the clinic for an additional visit (Visit 3) 90 days following Visit 2 to undergo specular microscopy and other safety evaluations.

Following the screening visit, eligible subjects will be randomly assigned a study eye (right eye=OD or left eye=OS) and study medication (active or placebo). Following dose administration, adverse events will be monitored. Safety assessments of BCVA, IOP, biomicroscopy, and external eye exam, will be performed on both eyes 60 to 90 minutes post dosing.

All subjects who are randomized and who receive the study medication on Day 1 will be followed up with a phone call to on Day 2-5 for safety assessment. A subset of subjects will return to the clinic for Visit 3, which is 90 days following Visit 2, for specular microscopy with all of the safety assessments.

2.3 Schedule of Assessments

The complete schedule of assessments for this study is shown in [Table 1](#) of the study protocol (see Protocol No. AG920-CS303 version 1.0, Page 11).

2.4 Randomization

As stated in the protocol, a randomization schedule generated by the Sponsor or designee will be used to assign subjects to each of the two treatment groups with a 2:1 allocation ratio to receive AG-920 or matching placebo. Subjects will also be randomized to study eye (OD or OS).

Study medication will be packaged and labeled identically in order to maintain the integrity of the double mask. The appearance of the blow fill seal vials for the AG 920 and matching placebo dosage forms are indistinguishable.

The container-closure system to be used for the AG-920 and Placebo in this clinical study is a 0.5 mL low-density polyethylene (LDPE) resin blow fill seal vial. There are 5 vials inside an aluminum foil pouch.

[REDACTED]

Each eligible subject will be assigned to one of the prepackaged cartons available at a site. The kit number associated with the prepackaged carton will be recorded on the CRF for this subject. Actual treatment assignments will be masked to the Investigator, the clinical study team (Sponsor, personnel involved in day to day study management, Monitors, Data Managers, and Statisticians), and the subjects.

Only in case of medical emergency or occurrence of adverse events that warrant unmasking in the opinion of the Investigator, will the treatment assignment(s) be unmasked and made available to the Investigator and the Sponsor Safety Officer. In the absence of medical need, the randomization code will not be available to the above personnel until after the study is completed and the database is locked.

2.5 Sample Size Estimation

The study is intended to enroll a total of 240 subjects in a 2:1 ratio of 160 subjects for AG-920 treatment and 80 subjects for placebo. This sample size is driven by the minimal safety exposure required for a regulatory marketing application.

2.6 Efficacy and Safety Measurements

Since this study is primarily a Phase 3 safety study, no efficacy assessments will be performed or defined.

Safety will be assessed through subject early terminations, adverse events, and changes in best corrected visual acuity (BCVA), IOP, biomicroscopy and external eye exam, heart rate and blood pressure, and concomitant medications. Changes in corneal health will be assessed through specular microscopy in a subset of patients.

2.6.1 Primary efficacy measure

Not applicable.

2.6.2 Secondary efficacy measure

Not applicable.

2.6.3 Safety measures

Adverse events (AEs) are recorded at each visit and at the follow-up phone call. When applicable, adverse events will be noted specifically in association with the study and fellow eyes.

Best corrected visual acuity (BCVA), IOP, and biomicroscopy (slit lamp) and external eye exam are performed at each visit, including at Visit 3 for the subset of subjects who participate in the specular microscopy test. Specular microscopy will be collected for the subset of subjects at Screening and at Visit 3.

A urine pregnancy test will be performed at screening for all female subjects of child-bearing potential.

2.6.4 Other measures

Concomitant medications associated with the treatment of the study and fellow eyes will be specifically noted as such.

2.7 Drug Concentration and PK Measurements

No drug concentration measures will be taken in this study.

2.8 Handling of Missing, Incomplete, and Repeat Data

There are no efficacy parameters in this study.

For safety parameters, missing or invalid data will be treated as missing for the corresponding assessment of a visit.

All data records are identified by study visit and/or assessment time point. Should repeated data records exist within a study visit and/or assessment time point, the first valid data record will be utilized for any statistical analyses of the corresponding study visit and/or assessment time point. All existing data records including the repeat data records in the study database will be presented in data listings and CRF data tabulations.

Any resultant incomplete or missing data of safety parameters will be treated as missing in the statistical analyses involving these parameters.

2.9 Statistical Methods

Unless specified otherwise, SAS® Version 9.0 or higher will be utilized to perform the statistical analyses of efficacy and safety measures.

Categorical variables will be summarized in general using frequencies and percentages, whereas continuous variables will be summarized in general using descriptive statistics of number of observations (n), mean, standard deviation (SD), minimum (Min), median, and maximum (Max).

In both data listings and CRF domain data tabulations, subject ID will consist of site number plus the subject screening number in the format of XXX-YYY, where XXX denotes the site number and YYY the subject's screening number within the site.

2.9.1 Primary efficacy analysis

Not applicable.

2.9.2 Secondary efficacy analysis

Not applicable.

2.9.3 Safety analysis

Treatment Exposure

Frequencies of exposure to the study medication will be calculated based on the number of drops the subject has received over the course of the study. Frequencies of exposure will be categorized as the following: 1 drop and 2 drops. Frequencies of exposure will be summarized by treatment for the safety population defined in Section 3.1, as well as by gender.

Compliance rates will be calculated by dividing the number of drops received by the number of drops that should have been given during the application of dose. Compliance rates will be summarized.

Early Termination

Subject disposition will be summarized by treatment and will be listed for those subjects who are terminated early. This listing will include demographic variables, treatment assigned, number of drops received, termination date, and the primary reason for early termination.

Adverse Events

Adverse events will be coded for preferred terminologies using Medical Dictionary for Regulatory Activities (MedDRA). AEs will be grouped into pre-treatment AE, treatment-emergent AE, and post-treatment AE and will be reported separately, based upon the start date and time of the events and the start date and time of the treatment.

Adverse events will be defined as pre-treatment AEs if they occur prior to the treatment start date and time; as treatment-emergent AEs if they occur on or after the treatment start date and time and before the next day; and as post-treatment AEs if they occur after the treatment date.

Frequency of treatment-emergent AEs will be calculated for each body system, by preferred terminology, by treatment group, for number of subjects and percentage reporting the event. The severity of the adverse events and the relationship to the investigational product will be summarized for each body system and preferred terminology by treatment group. Withdrawals due to adverse events will be summarized for each body system and preferred terminology by treatment group and will be listed with demographic variables for individual subjects.

Serious adverse events (SAE) (including deaths) will be listed for individual events.

Narratives will be provided for all deaths, non-fatal serious adverse events, and subjects withdrawn due to adverse events.

Best Corrected Visual Acuity (BCVA)

BCVA will be summarized in logMAR units by treatment for the screening (pre-dose) and Day 1 (post-dose), using number of observations, mean, standard deviation, minimum, median, and maximum values. The analysis will be based on the safety population defined in [Section 3.1](#).

For both study eye and fellow eye, changes in BCVA at post-dose from screening (pre-dose) will be analyzed for differences between AG-920 and placebo groups, using analysis of covariance (ANCOVA), with the pre-dose measurement as the covariate. Any BCVA changes of >3 lines from baseline will be flagged.

Intraocular Pressure (IOP)

Mean or median IOP values observed at a time point will be summarized in mmHg units by treatment for the screening (pre-dose) and Day 1 (post-dose), using number of observations, mean, standard deviation, minimum, median, and maximum values. The analysis will be based on the safety population defined in Section 3.1. Subjects who participated in the specular microscopy subset will also have IOP measured at Visit 3.

IOP measurements can be performed using a Tonopen® or Goldmann Tonometer. If a Goldmann tonometer is used, then two consecutive IOP measurements of each eye will be obtained. If the two measurements differ by more than 2 mm Hg, a third measurement should be obtained. IOP will be analyzed as the mean of two measurements or as the median of three measurements.

For both study eye and fellow eye, changes in IOP at post-dose from screening (pre-dose) will be analyzed for differences between AG-920 and placebo groups, using analysis of covariance (ANCOVA), with the pre-dose measurement as the covariate.

Biomicroscopy (Slit Lamp)

Total severity scores of biomicroscopy (slit lamp of seven items on grading scale, including lid erythema, lid edema, conjunctiva hyperemia, conjunctiva edema, corneal edema, anterior chamber cells, and anterior chamber flare) will be summarized and analyzed individually by treatment for the screening (pre-dose) and Day 1 (post-dose), and Visit 3 (for specular microscopy subjects) using number of observations, mean, standard deviation, minimum, median, and maximum values. The analysis will be based on the safety population defined in [Section 3.1](#).

For both study eye and fellow eye, changes in the total severity score at post-dose from screening (pre-dose) will be analyzed for differences between AG-920 and placebo groups, using analysis of covariance (ANCOVA), with the pre-dose measurement as the covariate.

Specular Microscopy

Endothelial cell count (and corneal morphology) will be summarized by continuous summaries. Mean and mean changes in data from the reading center from specular microscopy at baseline and 90 days post dosing from screening will be reported by treatment groups. The imaging parameters of Cell Density (CD), Coefficient of Variation (CV), Hexagonality (HEX) and Average Number of Cells (NUM) will all be reported variables from the central reading center.

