6.3 Visit 1 (Screening) – Day -2 to 0/1

Visit 1 may be combined with Visit 2 in order to accommodate clinic logistics. If both visits are combined, Visit 1 will last anywhere from 1-3 hours. If topical anesthetic drops are used to assess IOP, subject must wait at least 1 hour before IMP treatment. Topical anesthetic drops may cause a mild stinging or burning sensation upon instillation.

6.4 Visit 2 (Randomization/Treatment) – Day 1

Visit 2 must occur within 3 days of Visit 1 (Screening) if it is not performed on the same day as Visit 1. As noted in Section 6.3, Visit 1 and Visit 2 may be performed on the same day for clinic logistics. If a topical anesthetic is used to measure IOP at Screening (Visit 1), there must be at least a 1-hour interval post-anesthetic drops prior to treatment with IMP. At Visit 2, subjects are expected to be in the clinic for 60 to 90 minutes post dose.

6.4.3

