8.3 Adverse events¹

All AEs occurring after the first dose of IMP and throughout the remainder of the study period (Follow-up Phone Call; Visit 3 for subjects participating in specular microscopy) will be considered TEAEs and must be documented on the relevant Electronic Data Capture (EDC) pages and in the source documents. Whenever possible, the diagnosis, if available, and not the symptoms should be reported as the AE. AEs and Serious Adverse Events (SAEs) will be coded according to the Medical Dictionary for Regulatory Activities (MedDRA).

Documentation of adverse events/adverse reactions includes start date and stop date, severity, action(s) taken, seriousness and outcome.

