8.3.1 Adverse Event (AE) definitions

An *AE* is any untoward medical occurrence in a subject or clinical investigation subject, temporally associated with the use of a medicinal product, whether or not considered related to the medicinal product.

Note: An AE can therefore be any untoward or unfavorable medical occurrence in a human subject, including any abnormal sign (for example, abnormal physical exam or laboratory finding), symptom, or disease, temporally associated with the subject's participation in the research, whether or not considered related to the subject's participation in the research.

Any untoward or unfavorable medical occurrence in a human subject, including any abnormal sign (for example, abnormal physical exam or laboratory finding), symptom, or disease, temporally associated with the subject's participation in the research, whether or not considered related to the subject's participation in the research will be documented.

Events meeting the definition of an AE include:

- Exacerbation of a chronic or intermittent pre-existing condition including either an increase in frequency and/or intensity of the condition
- New conditions detected or diagnosed after study drug administration even though it may have been present prior to the start of the study
- Signs, symptoms, or clinical sequelae of a suspected interaction
- Signs, symptoms, or clinical sequelae of a suspected overdose of either study drug or a concomitant medication (overdose per se will not be reported as an AE/SAE).

¹ Note: This section is referenced to 21 CFR 312.32 (IND safety reports), updated as per "Investigational New Drug Safety Reporting Requirements for Human Drug and Biological Products and Safety Reporting Requirements for Bioavailability and Bioequivalence Studies in Humans (Fed Reg 2010: 75 (188): 59935-59963).

Events that do **not** meet the definition of an AE include:

- Medical or surgical procedure (e.g., endoscopy, appendectomy); the condition that leads to the procedure is an AE
- Situations where an untoward medical occurrence did not occur (social and/or convenience admission to a hospital)
- Anticipated day-to-day fluctuations of pre-existing disease(s) or condition(s) present or detected at the start of the study that do not significantly worsen
- The disease/disorder being studied, or expected progression, signs, or symptoms of the disease/disorder being studied, unless rescue medication or other medical treatment is required.

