5.3 Adverse Events

An overall summary of AEs reported in this study will be provided in Table 4.1.1 for study participants and in Table 4.1.2 for the safety population. The incidences of subjects reporting pre-treatment AE will be reported in Table 4.2.1 for the pre-randomization period and in Table 4.2.2 for the treatment-emergent AEs by treatment. Those treatment-emergent AE by preferred terminology that are reported by more than 5% of subjects in any individual treatment group will be tabulated in Table 4.2.3.

Incidences of subjects reporting treatment-emergent AEs (TEAEs) will also be tabulated by treatment for the TEAEs associated with the study eye in Table 4.2.5 and for the TEAEs associated with fellow eye in Table 4.2.6.

Incidences of subjects reporting treatment-emergent AEs will also be tabulated by onset time (on-treatment day vs. off-treatment day) in Table 4.3.1 for all TEAEs, and in Table 4.3.2 for the TEAEs associated with the study eye, and in Table 4.3.3 for the TEAEs associated with the fellow eye.

The severity of the treatment-emergent AEs and the relationship to the investigational product will be summarized in Table 4.4.1.

Treatment-emergent AEs associated with early terminations and serious AEs will be summarized by preferred term, respectively, in Table 4.4.2 and Table 4.4.3 for all TEAEs, in Table 4.4.4 and Table 4.4.5 for the TEAEs associated with the study eye, and in Table 4.4.6 and 4.4.7 for the TEAEs associated with the fellow eye.

Details of AEs associated with both study and fellow eyes will be listed for each subject (Listing 6)

Details of AEs associated with early terminations will be listed for each subject (Listing 7). SAEs, including deaths, will be listed (Listing 8).

Narratives will be presented for all deaths, non-fatal serious adverse events, and subjects withdrawn due to adverse events.

Female pregnancy results will be listed (Listing 9).

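### SAP 2.9.3 classes adverse events by start time alone, so an event that began before the drop and worsened after it can be left out of the treatment-emergent tables

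*SAP*

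**What the plan says.** SAP 2.9.3 puts each AE into one of three classes, "based upon the start date and time of the events and the start date and time of the treatment". The pre-treatment class is set by this sentence: "Adverse events will be defined as pre-treatment AEs if they occur prior to the treatment start date and time". Events fall into the next class "as treatment-emergent AEs if they occur on or after the treatment start date and time and before the next day". Anything later is post-treatment. No criterion other than timing is given, and SAP 5.3 adds none.

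Protocol 8.3.1 lists among the events that count as AEs: "Exacerbation of a chronic or intermittent pre-existing condition including either an increase in frequency and/or intensity of the condition". It also lists: "New conditions detected or diagnosed after study drug administration even though it may have been present prior to the start of the study". A note at the end of protocol 8.3.1.3 excuses sites from recording a pre-dose condition as an AE at later visits only if it has stayed the same or got better.

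On recording, protocol 8.3 states: "Documentation of adverse events/adverse reactions includes start date and stop date, severity", followed by action taken, seriousness and outcome. Protocol 8.3.2.1 deals with end dates and ongoing events. Neither section says what to do with the record when an event already under way becomes worse.

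On reporting, SAP 5.3 states: "The incidences of subjects reporting pre-treatment AE will be reported in Table 4.2.1 for the pre-randomization period". The incidence, study-eye, fellow-eye, onset-time, severity and relationship, discontinuation and SAE tables that follow are all titled as treatment-emergent.

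**The concern.** The protocol treats worsening as an adverse event in its own right. The SAP asks only when the event started. If the two are joined through a single record that keeps its original onset, a sign present before the drop that becomes more severe after it is counted as something that happened before treatment.

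TEAEs, and withdrawals due to them, are primary endpoints (protocol section 2). A classification that depends on how each site dates a worsened event leaves part of the main safety result to local habit. The effect runs one way: it can take events out of the treatment-emergent tables but cannot add any. If AG-920 did aggravate existing signs, the arm with more worsening would lose more events, and the contrast with vehicle would shrink.

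**Working it through.** There is no figure in the plan to reproduce on this point. The check is a comparison of text, followed by the arithmetic of one subject.

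**Inputs**
- Classification by event start against treatment start: SAP 2.9.3.
- Exacerbation counts as an AE: protocol 8.3.1.
- Only stable or improved pre-dose conditions are exempt from recording: note in protocol 8.3.1.3.
- Record content (start, stop, severity), with no rule for worsening: protocol 8.3 and 8.3.2.1.
- Group sizes 160 and 80: SAP 2.5. Check: 240 × 2/3 = 160 and 240 × 1/3 = 80.
- Cut-off of more than 5% in either arm for Table 4.2.3: SAP 5.3.

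**Step 1: one event, two ways of dating it.** Take a sign that is mild before the drop and moderate 60 minutes after it.

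| How the site records it | Class under SAP 2.9.3 | Where it is tabulated |
|---|---|---|
| One record, original onset kept, severity updated | Pre-treatment | Table 4.2.1 |
| New record dated from the worsening, on the dosing day | Treatment-emergent | Tables 4.2.2 onward |

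Both entries are compatible with the readable text. Under the first, the event is missing from Tables 4.2.2, 4.2.3, 4.2.5, 4.2.6, 4.3.1 to 4.3.3 and 4.4.1 to 4.4.7, wherever it would otherwise have qualified.

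**Step 2: a condition first found after dosing.** This case is weaker. Protocol 8.3.1 calls it new and ties it to detection after study drug, so dating it from detection is the natural reading, and the SAP rule then makes it treatment-emergent if it is found on the dosing day. It would be filed as pre-treatment only if the site entered a presumed earlier onset. A stated convention removes the doubt.

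**Step 3: size per affected subject.**
- AG-920: 1/160 = 0.625%, or 0.63 percentage points.
- Vehicle: 1/80 = 1.25 percentage points.

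The documents give no frequency. Purely as a scale, if 1 to 4 AG-920 subjects were affected (an assumption), the rate would move by 1/160 = 0.63 to 4/160 = 2.5 points.

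**Step 4: effect at the 5% cut-off.**
- AG-920: 0.05 × 160 = 8, so a term needs 9 subjects (9/160 = 5.6%). Removing one gives 8/160 = 5.0%, which is not above 5%.
- Vehicle: 0.05 × 80 = 4, so a term needs 5 subjects (5/80 = 6.25%). Removing one gives 4/80 = 5.0%.

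A term exactly at the threshold in one arm would therefore leave Table 4.2.3 through one reclassified subject, unless the other arm exceeds 5%.

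**The case against.** The case on the other side is substantial, and most of it stands.

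- **Misfiling is not automatic.** A reader might infer that the SAP files every worsened or later-detected event as pre-treatment. It does so only if the original onset is kept as the start. Protocol 8.3.1 makes the exacerbation itself the AE, and the note in 8.3.1.3 implies that a worsened condition is recorded at the later visit. A site that dates it from the worsening gets the right class for a dosing-day event. This stands and limits the point to what can happen.
- **The SAP does not contradict the protocol's TEAE definition.** Protocol 8.3 and 9.4.8 also define TEAEs by occurrence after the first dose, without a worsening clause. The mismatch is with the protocol's definition of an AE. This stands.
- **The events do not vanish.** Tables 4.1.1 and 4.1.2 and the Data 5.1 listing cover AEs in general, Listing 6 covers eye events and Listing 8 covers serious ones. Slit-lamp severity, BCVA and IOP are analysed as change from pre-dose for each eye (SAP 2.9.3), whatever the AE class. This stands.
- **The obvious scenario is weak.** Protocol 6.3 says of the drops used for tonometry: "Topical anesthetic drops may cause a mild stinging or burning sensation upon instillation". A reader might infer that this discomfort would run into, and hide, stinging from AG-920. But the sensation is tied to instillation, and protocol 6.3 and 6.4 require at least an hour before dosing, so stinging after AG-920 would ordinarily be a new event. Subjects with current ocular inflammation or allergy symptoms are also excluded (protocol 4.2). This stands and suggests small numbers.
- **A convention may exist elsewhere.** CRF completion instructions, protocol Appendix 1 and the SAP table shells are not in the readable text. This cannot be ruled out.

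None of this puts a worsening rule into the SAP. The note in protocol 8.3.1.3 says that a worsened condition should be recorded, but not with which start date, and start is the only thing SAP 2.9.3 looks at. SAP 5.3 plans a pre-treatment AE table, so pre-dose records able to absorb a later worsening are expected.

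**Conclusion.** The concern holds in a limited form. SAP 2.9.3 states a rule based on start time alone, the protocol counts worsening as an AE, and no readable text connects the two. An AE kept on one record with a pre-dose start that worsens after the drop can be left out of all the treatment-emergent tables, so the TEAE rate could be understated, by 0.63 points per affected AG-920 subject or 1.25 per vehicle subject.

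This rests on two conditions: that some events begin before the drop and worsen after it, and that a site keeps the original onset. The documents quantify neither. In healthy subjects with at most a few days between screening and dosing, the number is probably small.

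A reader might infer that the AG-920 ocular TEAE rate will be understated by a known amount, or that only ocular signs are affected. The documents support neither: there is no frequency to work from, and the rule applies to any AE. It should be corrected because it touches a primary endpoint and costs very little to put right.

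**What to change.** Before unmasking:

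- In SAP 2.9.3, extend treatment-emergent to include an AE or pre-existing condition that increases in severity or frequency at or after the first drop. Define pre-treatment as starting before the first drop and not worsening afterwards. Use the same wording in SAP 5.3.
- State, in the SAP and the CRF completion instructions, that a post-dose worsening is entered as a new record dated from the worsening, with its own severity, and that a condition first detected after dosing is dated from detection.

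The SAP's closing of the treatment-emergent window at the end of the dosing day is a separate issue, and this change leaves it as it is.

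The cost is a sentence or two in the SAP and a line in the CRF instructions. If AE records already exist, those with a pre-dose start need one check while treatment is still masked. The downside is that a few events of screening origin may enter the treatment-emergent tables. The same rule applies to both arms.
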